3.2 Study Population

Individuals with histologically or cytologically confirmed stage II-IV epithelial ovarian, peritoneal, or fallopian tube carcinoma (collectively referred to as ovarian cancer) who have completed primary surgery and chemotherapy within one to six months of screening, and are in clinical remission (no clinical evidence of disease on exam and normal CA-125 level) will be eligible. Individuals must be physically able to undertake a moderate exercise program. Individuals will be excluded if they have contraindications to initiating a training program (75), or if they already exercise >90 minutes per week of moderate intensity. Persons with peripheral neuropathy and lower extremity edema will not be excluded, but will be evaluated by their oncologist and the exercise physiologist for safety.

3.3 Study Design

Individuals with stage II-IV ovarian cancer (N=98) who have completed primary treatment within one to six months and are in clinical remission will be randomized in a 1:1 ratio to a 24-week home-based exercise program or wait-list control. The exercise prescription will consist of 150 minutes of moderate aerobic exercise (the equivalent of brisk walking or higher intensity) per week, with weekly telephone-based support by an exercise physiologist. The control group will perform their usual activities and will be offered the exercise intervention after 24 weeks. Baseline and 24-week assessments will include validated questionnaires assessing distress and health-related quality of life, serum levels of IL-6 and VEGF, salivary cortisol levels measured at bedtime for three consecutive days, and 24-hour urinary norepinephrine levels. Participants will also complete questionnaires at 12 weeks to provide additional longitudinal data. Adherence to the intervention will be assessed by daily activity logs, actigraphs, and completion of weekly telephone calls.

3.3.1 Primary Endpoints

1. Distress – mean change from baseline to 24 weeks between the exercise intervention and control group in the Perceived Stress Scale, and in the Hospital Anxiety and Depression Scale anxiety and depression subscales.
2. Quality of Life – mean change from baseline to 24 weeks between the exercise intervention and control groups in the 36-item Short Form Health Survey - Physical Component Score.
3. Biomarkers of angiogenesis- mean change from baseline to 24 weeks between the exercise intervention and control group in mean levels of IL-6, VEGF.
4. Nocturnal cortisol (biomarker of chronic stress) – mean change from baseline to 24 weeks between the exercise intervention and control group in mean evening cortisol level.

3.3.2 Exploratory Endpoints

1. Urinary norepinephrine- mean change from baseline to 24 weeks between the exercise intervention and control group in mean 24-hour urine norepinephrine level.
2. Mean change in outcomes (distress, Quality of Life, biomarkers) by category of exercise adherence (Percent of participants who exercised: ≥ 150 minute per week ($\geq 100\%$ of goal), 120-149 minutes per week, ($\geq 80\%$ of goal), 90-119 minutes per week ($\geq 60\%$ to $< 80\%$ of goal), 60-89 minutes per week ($\geq 40\%$ to $< 60\%$ of goal), 30-59 minutes per week ($\geq 20\%$ to $< 40\%$ of goal), < 30 minutes per week ($< 20\%$ of goal).
3. Correlations of levels of distress or Quality of Life with changes in biomarkers

3.3.3 Safety Endpoints

1. Serious adverse events and total adverse events attributable to the exercise intervention will be reported.

3.4 Estimated Accrual: 98 participants

3.5 Name of Sponsor/Funding Source: National Cancer Institute

4.0 SAFETY CONSIDERATIONS

4.1 Stopping Rules

N/A – the risk of serious adverse events with moderate exercise is very low. There is a <0.1% chance of a myocardial infarction and <0.02% chance of sudden death in a population at high risk for cardiovascular disease during a maximal treadmill protocol; the risks in this study will be considerably less, because we are screening participants so that only those without contraindications to exercise testing and initiating an exercise program will be eligible to participate. In addition, participants will be performing exercise at moderate intensity, and not at maximal effort, and will be performing exercises of their own choosing (under close guidance by the exercise physiologist).

4.2 Safety Measures

Individuals will be instructed to stop exercise and contact their doctor if they have any of the following symptoms during exercise or after an exercise session:

- Disorientation, dizziness, blurred vision or fainting
- Sudden onset of nausea, vomiting
- Unusual or sudden shortness of breath
- Irregular heartbeat, palpitations, chest pain
- Leg/calf pain, bone pain, unusual joint pain or pain not caused by injury
- Muscle cramps or sudden onset of muscular weakness or fatigue

The most common risks of exercise include fatigue and muscle soreness, and possibly joint or skeletal injury. These risks are reduced by proper warm-up/cool down periods, conservative and individual exercise prescriptions and progression, and careful education about ways to reduce injury by an experienced exercise physiologist. Musculoskeletal injuries will be assessed by one of the study clinicians. Individuals with a suspected serious musculoskeletal injury as a result of exercise will be instructed to be evaluated by their personal physician or to be evaluated at urgent care or the emergency department. Subsequent exercise will either be held to allow for recovery, or modified, depending on the nature of the injury and physician assessment. If a medical issue develops which is not related to exercise, the exercise prescription will also be modified as needed.

5.0 SUBJECT ELIGIBILITY

5.1 Inclusion Criteria

5.1.1 Histologically or cytologically confirmed stage II-IV primary epithelial ovarian, fallopian tube, or peritoneal cancer. If site of origin cannot be specified, carcinoma of Mullerian origin may be included if most consistent with ovarian/fallopian tube/peritoneal origin rather than uterine origin. The following histologic epithelial cell types are eligible: serous adenocarcinoma, endometrioid adenocarcinoma, mucinous adenocarcinoma, clear cell carcinoma, mixed epithelial carcinoma, transitional cell carcinoma, malignant Brenner's tumor, undifferentiated carcinoma, carcinosarcoma, or adenocarcinoma not otherwise specified. Individuals with neoplasms of low malignant potential (borderline tumors) are not eligible.

5.1.2 Subjects must have no evidence of disease, as defined by their treating oncologist, and with normal CA-125 (≤ 35).

5.1.3 Subjects must have completed primary surgery and adjuvant chemotherapy for treatment of ovarian, fallopian tube, or peritoneal cancer within one to six months of screening. Maintenance therapy will be allowed as long as the participant is in clinical remission— including hormonal agents, anti-angiogenesis agents, PARP inhibitors, and immunotherapy. Prior radiation therapy is allowed, as long as it has been completed within one to six months of screening. Subjects may have received prior therapies (including surgery, chemotherapy, radiation therapy) for other malignancies in the past.

5.1.4 Subjects must be 18 or older.

5.1.5 ECOG status of 0, 1, or 2. See Appendix B.

5.1.6 Pregnancy and the need for contraception:
N/A – participants with ovarian cancer have undergone hysterectomy with removal of ovaries and tubes as part of surgical treatment, and therefore do not have the potential to become pregnant.

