7.3 Concomitant Medication and Supportive Care Guidelines

All participants on either arm of the study may receive any care deemed beneficial by themselves or their treating physicians. They may take any medications or treatments indicated for concomitant medical conditions. Participants experiencing muscle soreness or discomfort as a result of exercising may take supportive over-the-counter medications including acetaminophen, non-steroidal anti-inflammatory drugs, and other analgesics (as long as they have not been instructed by their doctor to avoid those medications due to medical contraindications) or any medications prescribed by their physician. They may also apply ice or heat for symptomatic relief. In the event of a suspected injury, participants will be instructed to seek medical evaluation and treatment as indicated.

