9.0 SUBJECT DISCONTINUATION FROM STUDY

Subjects may be removed from this study at any time at their discretion. Subjects may also be removed from this protocol if they develop any untoward side effects from the study intervention.

Cancer recurrence does not mandate study discontinuation. If a subject develops cancer recurrence, they may still continue on the study if they are willing and able. Exercise is safe for individuals with cancer who are undergoing active treatments including chemotherapy. The exercise physiologist may alter their exercise prescription as needed based on the individual's functional ability and medical condition. If a participant desires to discontinue the study, she may discontinue the study at any time. If an individual desires to stop exercising but is willing to complete study assessments, she will complete originally planned study assessments (including clinic visit) at the originally specified time points.

An explanation for discontinuing the study is recorded for each subject discontinuing the study on the appropriate CRF/eCRF. Treatment in this study must be discontinued for any of the following reasons:

- if the PI decides to stop the study;
- at Investigator's discretion;
- at the subject's request;
- Grade 4 or life-threatening toxicity (See Section 11, Adverse Events) attributable to study intervention

Target enrollment is 98 participants, accounting for up to 20% drop-out. Power calculations are based on 78 participants. Additional subjects may be enrolled in the study to replace individuals who have dropped out in order to achieve the goal of 78 participants completing the study.

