13.2 Primary/Secondary Endpoints/Hypotheses and Analytical Methods

Descriptive statistics will be performed for baseline data, and distributions of outcome measures will be characterized using scatterplots, histograms, and summary statistics (e.g., mean, median, standard deviation, quartiles, range) to identify extreme outliers. Outcome variables will be log-transformed if their distributions are not symmetric. We will also examine if these measurements are balanced between the study intervention groups. The primary assessment of the exercise intervention effects will compare the average change from baseline to 24-week follow-up outcome measures (such as SF-36 physical component score) between the exercise group and the control group. Analyses will be intention-to-treat. The generalized estimating equations (GEE) modification of linear regression will be used in order to model the relationship between the outcome measures and exercise intervention and to account for the correlation within individual data over time. The GEE model will adjust for the measurement time and other potential covariates. Prior to fitting the GEE model, logarithmic transformation will be applied (if appropriate) to the outcome data to achieve approximate normality and variance stabilization. Our statistical inference on each outcome will use the standard large-sample approximation, namely, two-sided Z-test and Z-confidence intervals based on the limiting Gaussian distribution. More specifically, for the primary comparison between exercise group *vs.* control group, let Y_{ij} be the outcome measure (or log-transformed if appropriate) of interest for participant i at time j , where j is 0 for baseline and 1 for 24 week follow-up, X_i be the indicator variable for the intervention status (1=intervention, 0=control) and Z_i represent a vector of other potential adjusting variables (such as age, BMI). The linear model is as follows:

$$E[Y_{ij}] = \alpha_0 + \alpha_1 j + \beta_0 X_i + \beta_1 X_i j + \gamma^T Z_i, \text{Var}[Y_{ij}] = \sigma^2 \text{ and } \text{Cov}[Y_{ij}, Y_{kl}] = \rho \text{ if } i = k \text{ and } j \neq l, \text{ and } 0 \text{ otherwise.}$$

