13.4 Randomization

After baseline assessments are complete, participants will be randomized with equal probability to the exercise intervention (N=49) or wait-list control (N=49). Randomization will be blocked on stage (stages II-IIIA vs. IIIB-IV) and body mass index (<30 kg/m² vs. \geq 30 kg/m²) and will use permuted blocks with random size.

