13.7 Exploratory Analysis

In exploratory subgroup analyses, we will apply the GEE models for the primary analysis given above to study the intervention effect on each of the primary outcomes among participants who developed (versus those who did not develop) recurrence over the course of the study. The GEE models will also be applied to additional exploratory subgroup analyses to assess the intervention effects on the primary outcomes by chemotherapy maintenance group (if the sample size is sufficient).

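### Anti-angiogenic maintenance is allowed while VEGF change is a primary endpoint, and the planned model cannot remove the noise that drug changes would add

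*Combined protocol and SAP*

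**What the plan says.** Section 5.1.3 allows maintenance therapy during clinical remission, "including hormonal agents, anti-angiogenesis agents, PARP inhibitors, and immunotherapy". Section 3.3.1 lists among the primary endpoints "Biomarkers of angiogenesis- mean change from baseline to 24 weeks between the exercise intervention and control group in mean levels of IL-6, VEGF".

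Treatment is not held fixed between baseline and week 24. Under section 7.3, participants in either arm "may receive any care deemed beneficial by themselves or their treating physicians". Under section 9.0, after a recurrence "they may still continue on the study if they are willing and able". I found no stable-treatment or washout rule for this drug class.

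On allocation, section 13.4 states: "Randomization will be blocked on stage (stages II-IIIA vs. IIIB-IV) and body mass index". Maintenance therapy is not a factor. In the section 13.2 model, the covariates Z "represent a vector of other potential adjusting variables (such as age, BMI") enter as a single time-constant term, with no product of Z and time. Section 13.7 adds exploratory subgroup analyses by recurrence, and a further one to "assess the intervention effects on the primary outcomes by chemotherapy maintenance group (if the sample size is sufficient"). The maintenance group is not defined, so it is unclear whether it covers anti-angiogenic agents. Section 8.1 records drug name, dose and frequency at the baseline and week-24 assessments.

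**The concern.** The trial admits a drug class aimed at the process that one of its seven primary endpoints is meant to measure. A participant who starts or stops such a drug between draws may show a VEGF change that has nothing to do with exercise. Even when this happens equally often in both arms, it widens the spread of the change scores. VEGF has little precision to spare: at a correlation of 0.65, the detectable difference in Table 1 is already 55% of the planning mean.

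The plan takes comparable care elsewhere. Section 8.1 collects diet data because diet may affect the biomarkers, and asks participants to avoid NSAIDs for 24 hours before the blood draw. Anti-angiogenic exposure gets no such handling in the VEGF analysis, and the adjusted model as written could not supply it.

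**Working it through.** **Inputs from the documents.** VEGF mean 192 and SD 158.2 pg/mL, 39 per arm, 80% power, type I error 0.05/7 (Table 1, section 13.3); two-sided Z-test (section 13.2).

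**Step 1: reproduce Table 1.** The multiplier is 2.690 + 0.842 = 3.532.

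- SD of change = 158.2 × √(2 × (1 − 0.65)) = 132.4.
- SE of the between-arm difference = 132.4 × √(2/39) = 30.0.
- Detectable difference = 3.532 × 30.0 = 105.9 pg/mL (Table 1: 105.8). The same formula gives 126.5 and 80.0 at correlations of 0.5 and 0.8, as printed.

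**Step 2: add drug changes.** Let a fraction f of each arm start or stop a drug between draws, shifting VEGF by D, all in the same direction. Variance of change becomes 132.4² + f(1 − f)D². Neither f nor D is in the documents; both are assumptions. D is taken as 96 and 192 (0.5 and 1 times the planning mean) and 158.2 and 316.4 (1 and 2 times the planning SD). At a correlation of 0.65:

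| f | D (pg/mL) | SD of change | Detectable difference | Power at 105.9 |
|---|---|---|---|---|
| none | – | 132.4 | 105.9 | 80% |
| 5% | 96 | 134.0 | 107.2 | 79% |
| 10% | 158.2 | 140.6 | 112.5 | 74% |
| 10% | 192 | 144.3 | 115.4 | 71% |
| 20% | 192 | 153.0 | 122.4 | 64% |
| 20% | 316.4 | 183.1 | 146.5 | 45% |

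**Step 3: chance imbalance.** If 4 more participants switch in one arm of 39 than in the other, the estimate moves by 4/39 × 158.2 = 16.2, or 4/39 × 316.4 = 32.5 pg/mL. The matching SEs (rows f = 10%, D = 158.2 and f = 20%, D = 316.4) are 140.6 × √(2/39) = 31.8 and 183.1 × √(2/39) = 41.5. The shift is therefore 0.5 to 0.8 SE, against the 2.69 SE needed for significance (86 to 112 pg/mL).

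**Step 4: what the stated model can do.** With both visits complete and an exchangeable correlation, the estimate of β₁ is the between-arm difference in the mean of Y at week 24 minus Y at baseline. A time-constant term γᵀZ cancels from that subtraction, so it changes neither the estimate nor its sandwich standard error. In one simulated data set (78 participants, GEE, an assumed drug-related VEGF change), adding the drug indicator as a main effect left β₁ at 21.8 and its SE at 40.0. Adding drug by time cut the SE to 30.9.

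**Step 5: how much a baseline indicator recovers.** As an illustration, suppose 20% use the drug at baseline, half of them stop and nobody starts. Switching adds 0.10 × 0.90 × D² = 0.09D². The baseline-use-by-time term removes 0.20 × 0.80 × 0.5² × D² = 0.04D², or 44% of it. Unplanned later starts are not captured.

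**The case against.** Randomisation protects the comparison, and this is the strongest reply. A reader might infer that drug changes could pass for an exercise effect, or that no VEGF result could be credited to exercise. The documents do not support either. Switching unrelated to arm enters the standard error, so type I error is approximately kept, and Step 3 shows that a plausible imbalance falls far short of significance. Nor is that imbalance an extra harm: it is one realisation of the variance already counted in Step 2. Switching that differs by arm is conceivable in an unblinded trial, but nothing in the documents points to it.

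A reader might also count steady users as a problem. The endpoint is change, so a constant offset largely cancels, and section 8.1 assays each participant's paired samples in the same batch. The documents say nothing about how these drugs affect serum VEGF or its assay, so no direction or mechanism is claimed here.

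The calculation has limits. At the low end the loss is negligible. A shift of 316 pg/mL exceeds the planning mean of 192, so it could not be an average fall. The work is on the raw scale, whereas section 13.2 would log-transform a skewed outcome.

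The plan also has partial safeguards: medication lists, balance checks on covariates (section 13.6), an open covariate list and the exploratory subgroups. These soften the gap. They do not close it, because the covariate list acts only through main effects, and the maintenance subgroup is undefined and conditional on sample size.

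**Conclusion.** The point holds as one of precision and interpretability for a single primary endpoint. The plan admits anti-angiogenic maintenance, lets treatment change between draws, and has no analysis that accounts for it in VEGF; its adjusted model could not do so even with maintenance use added.

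The size depends on two quantities that the documents do not give. Over 5% to 20% switching and shifts of 96 to 316 pg/mL, at a correlation of 0.65, the detectable difference rises from 105.9 to between 107.2 and 146.5 pg/mL, and power at the planned difference falls to between 79% and 45%. This does not make the VEGF comparison invalid. It makes a null VEGF result harder to read, and it leaves any later adjustment open to the charge of being post hoc.

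**What to change.** In section 13.2, for VEGF only, and before VEGF results are seen:

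- Add baseline anti-angiogenic use (yes/no, from the baseline medication record) and its interaction with time to the adjusted model. Current use is the right basis, because section 8.1 does not record planned therapy.
- Pre-specify a sensitivity analysis restricted to participants not using such a drug at baseline. The subset is defined before randomisation, so the comparison remains randomised.
- Tabulate use at both draws by arm. Handle changes after randomisation only in sensitivity analysis, not as a covariate in the main model.

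Eligibility is unchanged. The cost is some SAP wording, one variable derived from data already collected, one or two extra model terms, and lower precision in the restricted analysis. The baseline term recovers only part of the lost precision, as Step 5 of the working shows.

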5.1.7 Ambulatory

5.1.8 Ability to understand and the willingness to sign a written informed consent document.

5.1.9 Individuals participating in most other clinical trials are eligible provided their enrollment in the other trial does not impair their ability to participate in the physical activity interventions and study assessments required in this trial. The other clinical trial must not be a behavioral intervention trial.

5.2 Exclusion Criteria

5.2.1 Subjects who have had primary surgery, chemotherapy and/or radiation therapy within 4 weeks prior to screening. Subjects may have received other surgeries not performed for primary treatment (for example, removal of intraperitoneal port, laparoscopic cholecystectomy, etc.) within 1 month of screening as long as they do not have post-operative restrictions that would preclude participating in a moderate intensity exercise program once enrolled in the clinical trial.

5.2.2 Self-reported inability to walk at least 2 blocks (at any pace).

5.2.3 Prior brain metastasis is not an exclusion, as long as subject is in clinical remission.

5.2.4 Uncontrolled or concurrent illness including, but not limited to: unstable angina pectoris, recent (within six months) myocardial infarction, uncontrolled cardiac arrhythmia, uncontrolled congestive heart failure, hypertrophic obstructive cardiomyopathy, uncontrolled hypertension (systolic > 200, diastolic > 120), conditions (cardiovascular, respiratory, or musculoskeletal disease or joint problems) that preclude moderate physical activity. Subjects with a history of cardiac arrest, or those with moderate/severe aortic or mitral stenosis may be eligible if their treating physician determines that moderate physical activity is safe. Moderate arthritis that does not preclude physical activity is not a reason for ineligibility. Individuals with lymphedema or peripheral neuropathy will not be excluded. They will be evaluated by the exercise physiologist for safety and modifications to the exercise prescription will be made as appropriate.

5.2.5 Psychiatric illness/social situations that would limit compliance with study requirements.

5.2.6 Already physically active >90 minutes per week of moderate exercise.

[figure not shown]
6.0 SUBJECT REGISTRATION

Subjects will be registered by the Fred Hutch/UW Study Coordinator and entered into the Protocol Accrual Tracking System (PATS). A complete, signed, study consent and HIPAA consent are required for registration.

